## Clinical Investigational Plan

2. If these attempts are unsuccessful, a letter should be sent to the subject's last known address or the subject's general practitioner (GP) and a copy of this letter should be maintained in the subject's medical records.

Note: If a subject misses one or more of the scheduled follow up visits (inclusive of the assigned visit windows) without being lost to follow-up this will be considered as a missed visit. The subject may, therefore, still return for subsequent visits and will not be withdrawn from the study.

If there is a potential withdrawal in the study, please contact a member of the study team to see if there is anything that can be done to keep the subject in the study.

An analysis will be performed to compare demographics and key clinical characteristics for the subjects who have withdrawn and those who continue to be enrolled in the study. This analysis will be reported in the annual progress reports.

### **14.0 COMPLIANCE TO CIP**

#### **14.1 Adherence to the CIP**

A deviation is defined as an event where the clinical investigator, site personnel, sponsor or sponsor representative did not conduct the clinical study according to the Clinical Investigational Plan, IRB requirements or the Investigator Agreement. The investigator is not allowed to deviate from the CIP, except as specified under emergency circumstances.

In some cases, failure to comply with the CIP may be considered failure to protect the rights, safety and well-being of subjects, since the non-compliance exposes subjects to unreasonable risks. For example, failure to adhere to the inclusion/exclusion criteria: these criteria are specifically defined by the Sponsor to exclude subjects for whom the device is not beneficial and the use involves unreasonable risks. This may be considered failure to protect the rights, safety and well-being of the consented subject. Similarly, failure to perform safety assessments intended to detect AEs may be considered failure to protect the rights, safety and well-being of the consented subject. Investigators should seek minimization of such risks by adhering to the CIP.

Simultaneously, in the event that adhering to the CIP might expose the subject to unreasonable risks, the investigator is also required to protect the rights, safety and well-being of the subject by intentionally deviating from the requirements of the CIP, so that subjects are not exposed to unreasonable risks.

It is the responsibility of the investigator to provide adequate medical care to a subject consented for participation in a study.

Regulations require that the Investigator maintain accurate, complete, and current records, including documents showing the date of and reason for every deviation from the Clinical Investigational Plan.

Regulations require Investigators obtain approval from St. Jude Medical and the IRB [as required] before initiating changes in or deviations from the protocol, except when necessary to protect the life or physical well-being of a subject in an emergency. Under emergency

## Clinical Investigational Plan

circumstances, deviations from the CIP to protect the rights, safety and well-being of human subjects may proceed without prior approval of the sponsor and the IRB. Such deviations shall be documented and reported to the sponsor and the IRB as soon as possible, but no later than 5 working days.

Prior approval must be requested when the Investigator anticipates, contemplates, or makes a conscious decision to depart from the CIP, except when unforeseen circumstances are beyond the investigator's control (e.g. a subject who fails to attend a scheduled follow-up visit, a subject is too ill to perform a CIP-required test, etc.). All deviations, including those beyond the investigator's control, must be reported to the St. Jude Medical as soon as possible and to appropriate regulatory authorities in specified timelines (if appropriate). The Investigator is required to adhere to local regulatory requirements for reporting deviations to IRB.

Investigator will notify St. Jude Medical and the reviewing IRB within 5 working days of:

- Any deviation to protect the life or physical well-being of a subject in an emergency
- Any failure to obtain informed consent

### 14.2 Repeated and Serious Non-Compliance

In the event of repeated non-compliance or a one-time serious non-compliance, as determined by the Sponsor, a Clinical Research Associate or clinical representative will attempt to secure compliance by one or more of the following actions:

- Visiting the investigator
- Contacting the investigator by telephone
- Contacting the investigator in writing
- Retraining of the investigator

If an investigator is found to be repeatedly non-compliant with the signed agreement, the CIP or any other conditions of the clinical study, the Sponsor will either secure compliance or, at its sole discretion, terminate the investigator's participation in the clinical study.

### 15.0 AMENDMENTS TO CLINICAL INVESTIGATIONAL PLAN

Study related documents such as, the CIP, Informed Consent form and other subject information, or other clinical study documents will be amended as needed. Proposed amendments to the CIP will be agreed upon between the Sponsor and the coordinating investigator (if applicable). The amendment will identify the changes made and the reason for the changes. The amendments to the CIP and the subject's Informed Consent will be notified to, or approved by, the IRB and regulatory authorities, if required.

Any amendment affecting the subject requires that the subject be informed of the changes and a new consent be signed and dated by the investigator at the subject's next follow up.

### 16.0 INVESTIGATION SUSPENSION OR TERMINATION

The Sponsor reserves the right to stop the study at any stage, with appropriate written notice to the investigator. Possible reasons for early termination of the study by the sponsor, either at local, national or international level, may include, but are not limited to:

- The device / therapy fails to perform as intended

## Clinical Investigational Plan

- Occurrence of SAE which cannot be prevented in future cases
- Sponsor's decision
- Request from Regulatory bodies
- Request of IRB
- Concern for subject safety and welfare
- Failure to secure subject Informed Consent prior to any investigational activity
- Repeated non-compliance with this CIP or the Clinical Trial Agreement
- Inability to successfully implement this CIP
- Falsification of data, or any other breach of ethics or scientific principles
- Loss of or unaccounted use of investigational device inventory

The study will be terminated according to applicable regulations. The investigator may also discontinue participation in the clinical study with appropriate written notice to the Sponsor. Should either of these events occur, the investigator will return all documents to the sponsor; provide a written statement as to why the premature termination has taken place and notify the IRB. Follow-up for all consented subjects will be as per CIP requirements. An Investigator, IRB or regulatory authority may suspend or prematurely terminate participation in a clinical study at the investigational sites for which they are responsible.

If suspicion of an unacceptable risk to subjects arises during the clinical study or when so instructed by the IRB or regulatory authority, St. Jude Medical may suspend the clinical study as appropriate while the risk is assessed. St. Jude Medical will terminate the clinical study if an unacceptable risk is confirmed.

St. Jude Medical will consider terminating or suspending the participation of a particular investigational site or investigator in the clinical study if monitoring or auditing identifies serious or repeated deviations on the part of an investigator.

If suspension or premature termination occurs, the terminating party will justify its decision in writing and promptly inform the other parties with whom they are in direct communication. The Principal Investigator and St. Jude Medical will keep each other informed of any communication received from IRB or regulatory authority.

If for any reason St. Jude Medical suspends or prematurely terminates the study at an individual investigational site, St. Jude Medical will inform the responsible regulatory authority, as appropriate, and ensure that the IRBs are notified, either by the Investigator or by St. Jude Medical. If the suspension or premature termination was in the interest of safety, St. Jude Medical will inform all other Principal Investigators.

If suspension or premature termination of enrollment occurs, St. Jude Medical will remain responsible for providing resources to fulfill the obligations from the CIP and existing agreements for following up the subjects consented for participation in the clinical study, and the Investigator or authorized designee will promptly inform the consented subjects at his/her investigational site, if appropriate.

## Clinical Investigational Plan

### **17.0 RESUMING THE STUDY AFTER TEMPORARY SUSPENSION**

When St. Jude Medical concludes an analysis of the reasons for the suspension, implements the necessary corrective actions, and decides to lift the temporary suspension, St. Jude Medical will inform the Investigators, IRB, or regulatory authority, where appropriate, of the rationale, providing them with the relevant data supporting this decision. Concurrence will be obtained before the clinical study resumes from the IRB or regulatory authority where appropriate. If subjects have been informed of the suspension, the Principal Investigator or authorized designee will inform them of the reasons for resumption.

### **18.0 ADMINISTRATIVE REQUIREMENTS AND QUALITY ASSURANCE**

#### **18.1 Study Investigators**

The study will be conducted by qualified investigators who have been evaluated and have completed the required training related to implant and use of DRG Neurostimulation Systems.

#### **18.2 Institutional Review Board (IRB)**

Before study enrollment can begin, the Investigator must provide the Sponsor with a copy of the approval notice for the protocol and informed consent forms, signed by the committee Chairperson or designee. An Investigator shall report to the Sponsor, within 5 working days, a withdrawal of approval by the reviewing IRB of the Investigator's part of an investigation.

#### **18.3 Informed Consent**

Written Informed Consent will be obtained from all subjects before any study-related procedures are performed. All potential subjects must be properly informed as to the purpose of the study and the potential risks and benefits known or that can be reasonably predicted or expected. The Investigator will retain the original copy of the Informed Consent Form signed by the subject and a duplicate will be provided to the subject. Only the consent form approved by the IRB should be used.

### **19.0 DATA MANAGEMENT**

The Sponsor will be responsible for the data handling. The sponsor and/or its affiliates will be responsible for compiling and submitting all required reports to governmental agencies.

St. Jude Medical respects and protects personally identifiable information collected or maintained for this clinical trial. The privacy of each subject and confidentiality of his/her information will be preserved in reports and when publishing any data. Confidentiality of data will be observed by all parties involved at all times throughout the clinical trial. All data will be secured against unauthorized access.

Data will be captured in a validated electronic database management system hosted by St. Jude Medical. Only authorized site personnel will be permitted to enter data into the electronic data capture (EDC) system deployed by St. Jude Medical. An electronic audit trail will be used to track any subsequent changes of the entered data.

## Clinical Investigational Plan

### 19.1 Data Management Plan (DMP)

A detailed Data Management Plan will be established to ensure consistency of the data. This document will include procedures used for data review, database cleaning, and issuing and resolving data queries. If appropriate, the DMP may be updated throughout the study duration. All revisions will be tracked and document controlled.

Data will be captured in a validated electronic database management system hosted by St. Jude Medical. Only authorized site personnel will be permitted to enter data into the electronic data capture (EDC) system deployed by St. Jude Medical. An electronic audit trail will be used to track any subsequent changes of the entered data.

## 20.0 MONITORING

It is the responsibility of St. Jude Medical as the sponsor of the study to ensure the study is conducted, recorded, and reported according to the approved protocol, subsequent amendment(s), applicable regulations, and guidance documents. Monitoring will be conducted according to the St. Jude Medical Clinical Monitoring standard operating procedure.

Prior to beginning the study, St. Jude Medical will contact the investigator or designee to discuss the study and data requirements. A St. Jude Medical monitor will periodically review the subject records and associated source documents. The investigator shall make subject and study records available to the clinical monitor for monitoring.

Centralized monitoring will occur through routine internal data review. This monitoring is designed to identify missing and inconsistent data, data outliers, and potential protocol deviations that may be indicative of site non-compliance. On-site monitoring may occur at the discretion of the Sponsor.

## 21.0 REGULATORY INSPECTIONS

The investigator and/or delegate should contact St. Jude Medical immediately upon notification of a governmental agency inspection at the site. A clinical monitor or designee will assist the investigator and/or delegate in preparing for the audit.

An investigator, or any person acting on behalf of such a person with respect to the study, will permit authorized governmental agency employees, at reasonable times and in reasonable manner, to inspect and copy all records relating to the study.

An investigator will permit authorized governmental agency employees to inspect and copy records that identify subjects, upon notice that governmental agency has reason to suspect that adequate informed consent was not obtained, or that reports required to be submitted by the investigator, to the Sponsor or IRB have not been submitted or are incomplete, inaccurate, false or misleading.

## 22.0 DOCUMENT RETENTION

St. Jude Medical and the Principal Investigators will maintain the clinical study documents as required by St. Jude Medical, Inc. and applicable regulatory requirements. They will take measures to prevent accidental or premature destruction of these documents. The Principal

## **Clinical Investigational Plan**

Investigator or St. Jude Medical may transfer custody of records to another person/party and document the transfer at the investigational site or at St. Jude Medical's facility.

These documents must be retained by the investigational site for a period of 2 years after clinical study conclusion and made available for monitoring or auditing by St. Jude Medical's representative or representatives of the FDA and other applicable regulatory agencies. The Investigator must ensure the availability of source documents from which the information was derived.

### **23.0 DEVIATIONS FROM THE INVESTIGATION PLAN**

All deviations from the Investigational plan will be recorded on a worksheet and in the EDC system. In accordance with 21 CFR 812.150(a)(4), an Investigator shall notify the Sponsor and the reviewing IRB of any deviation from the investigational plan to protect the life or physical well-being of a subject in an emergency. Such notice shall be given as soon as possible, but in no event later than 5 working days after the emergency occurred. Except in such an emergency, prior approval by the Sponsor is required for changes in or deviations from a plan, and if these changes or deviations may affect the scientific soundness of the plan or the rights, safety, or welfare of human subjects, FDA and IRB in accordance with 812.35(a) also is required.

### **24.0 CLINICAL EVENTS COMMITTEE (CEC)**

A Clinical Events Committee (CEC) will be responsible for providing an independent review and adjudication of all subject deaths and adverse events. The CEC will review adverse events and determine device and/or procedure relatedness and whether serious or not (ADEs, SADEs, and SAEs). The CEC will base their final adjudication on the information provided on the case report forms, medical records, and their clinical knowledge and experience. The committee will consist of a minimum of three (3) members, comprised of pain specialists with experience in medical device implants/studies. The CEC will meet on an as-needed basis, at a minimum twice a year, to assess individual events in the study. [REDACTED]

### **25.0 PUBLICATION POLICY**

The results of the clinical study will be submitted for publication, regardless of the outcome. A 'Publication Agreement' will be signed between the Principal Investigator and the Sponsor either as a separate Publication Agreement or within the Clinical Trial Agreement. The International Committee of Medical Journal Editors (ICMJE) guidelines on publication will be followed ([www.icmje.org](http://www.icmje.org)). This study will be posted on ClinicalTrials.gov and results will be posted on ClinicalTrials.gov as required.

**Clinical Investigational Plan****APPENDIX A: ABBREVIATIONS**

Abbreviation	Term
AE	Adverse Event
CEC	Clinical Events Committee
CIP	Clinical Investigational Plan
CRPS	Complex Regional Pain Syndrome
DMP	Data Management Plan
DRG	Dorsal Root Ganglion Stimulation
eCRF	Electronic Case Report Form
EDC	Electronic Data Capture
ICMJE	International Committee of Medical Journal Editors
IPG	Implantable Pulse Generator
IRB	Institutional Review Board
ISO	International Organization for Standardization
MP	Monitoring Plan
NA	Not Applicable
PG	Pulse Generator
RDC	Remote Data Capture
SAE	Serious Adverse Event
SJM	St. Jude Medical
TENS	Transcutaneous Electrical Nerve Stimulation

ST. JUDE MEDICAL™

Study Document No: SJM-CIP-10113 Ver. E  
Study Name: TARGET (DRG) Post-Approval Study

## Clinical Investigational Plan

### APPENDIX B: CIP REVISION HISTORY

[REDACTED]

### APPENDIX C: DECLARATION OF HELSINKI

The most current version of the document will be followed.

[REDACTED]

[REDACTED]

## **Clinical Investigational Plan**

### **APPENDIX D: LIST OF CLINICAL INVESTIGATION SITES AND IRB**

A list of Clinical Investigational sites and IRB will be kept under a separate cover and is available upon request.

### **APPENDIX E: SAMPLE INFORMED CONSENT**

Sample Informed Consent form will be kept under a separate cover and is available upon request.

### **APPENDIX F: CASE REPORT FORMS**

Final Case Report Forms will be kept under a separate cover and are available upon request.

### **APPENDIX G: INSTRUCTIONS FOR USE**

IFUs will be kept under a separate cover and are available upon request.

1.0 SYNOPSIS OF STUDY DESIGN

1.1 Purpose of the Statistical Analysis Plan

This statistical analysis plan (SAP) is intended to provide a detailed and comprehensive description of the planned methodology and analysis to be used for the TARGET (DRG) post approval clinical investigation. [REDACTED]

1.2 Clinical Investigation Objectives

The primary objective of this study is to demonstrate that the proportion of serious adverse events at 12 months for subjects who receive the permanent DRG IPG is lower than a pre-specified performance goal. The secondary objectives of this study are to evaluate the change in overall pain intensity, change in physical function and change in quality of life at 12 months.

1.3 Clinical Investigation Design

This study is a prospective, multicenter, single arm, observational, post-approval study with follow-ups at 1, 3, 6 and 12 months post-permanent implant. [REDACTED]

[REDACTED]

[REDACTED]

After the subject signs the informed consent, s/he will be screened according to the inclusion/exclusion criteria and will undergo a baseline evaluation. Those subjects who meet the criteria for participation will undergo a trial of the DRG Neurostimulation System to assess response to DRG stimulation. For purposes of accounting, subjects are considered enrolled in the study only after they receive the trial system implant. Subjects who fail the trial procedure are considered as screen failures. Only subjects who report a 50% or greater reduction in overall pain intensity through direct patient-reported percentage of pain relief at the of trial evaluation period will receive the permanent implant. Device activation will occur according to the site's standard of care and may occur at the time of permanent system implant. Subjects will then return to the office for follow-up at 1, 3, 6 and 12 months post-permanent implant.

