## Clinical Investigational Plan

	

Change from baseline to 12 months post-permanent implant for quality of life measured using the PROMIS Global Health Scale

Descriptive Endpoints:	
Safety
 

Proportion of subjects with device, procedure or stimulation-related SAEs and non-SAEs among subjects who receive the permanent implant

Proportion of subjects who have AEs related to the trial implant procedure among subjects who fail the trial neurostimulator phase

Summary of procedure-related SAEs and non-SAEs by implant experience

 
Effectiveness
 

Change from baseline to 1, 3, and 6 months post-permanent implant for overall pain intensity measured using the Visual Analog Scale (VAS)

Change from baseline to 1, 3, and 6 months post-permanent implant for physical function measured using the PROMIS-29 Profile

Change from baseline to 1, 3, and 6 months post-permanent implant for quality of life measured using the PROMIS Global Health Scale

Change from baseline to 1, 3, 6 and 12 months post-permanent implant for neuropathic pain measured using the Neuropathic Pain Scale (NPS)

Change from baseline to 1, 3, 6 and 12 months post-permanent implant for sleep disturbance, anxiety, depression, fatigue, ability to participate in social roles and activities, pain interference and pain intensity measured using the PROMIS-29 Profile

Patient Global Impression of Change (PGIC) at 1, 3, 6 and 12 months post-permanent implant

Design:	This study is a prospective, single arm, observational post-approval study. Study follow-ups will occur at 1, 3, 6, and 12 months post-permanent implant.
Devices used:	DRG Neurostimulation System with Axium or Proclaim DRG Implantable Pulse Generator
Study Population	A maximum of 426 adult subjects with moderate to severe chronic, intractable pain of the lower limbs due to CRPS types I and II will undergo a trial of the neurostimulator system at up to 45 study sites in the United States.
Inclusion/Exclusion Criteria	
Inclusion Criteria
 

Subject is male or female <math>\geq</math> 22 and <math>\leq</math> 75 years of age.

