**Clinical Investigational Plan**

at up to 45 centers in the United States. A maximum of 426 subjects will be enrolled to achieve 319 subjects with a permanently implanted system, which will account for expected attrition, to yield 287 subjects for the primary analysis at 12 months post-implant (See Section 10.9 Sample Size for full details). After the last subject with a permanently implanted device reaches the 12-month study visit or crosses the 12-month study visit window, the endpoint analysis will be conducted and reported to the FDA.

After the subject signs the informed consent, s/he will be screened according to the inclusion/exclusion criteria and will undergo a baseline evaluation. Those subjects who meet the criteria for participation will undergo a trial of the DRG Neurostimulation System to assess response to DRG stimulation. Only subjects who report a 50% or greater reduction in overall pain intensity through direct patient-reported percentage of pain relief will receive the permanent implant. Device activation will occur according to the site's standard of care and may occur at the time of permanent system implant. Subjects will then return to the office for follow-up at 1, 3, 6 and 12 months post-permanent implant. Figure 2 below outlines subject flow through the study.

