## 7.0 SUBJECT SELECTION

Subjects who meet all of the inclusion criteria and none of the exclusion criteria are eligible to participate in this study. All subjects in the clinical study (including system trial failures, those withdrawn from the clinical study and those lost to follow-up) will be accounted for and documented by assigning an identification code linked to their [REDACTED], alternative identification or

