### 9.1.5 Serious Adverse Device Effect (SADE).

## 9.2 Assessing, Recording and Reporting AEs

Safety surveillance within this study and the safety reporting both performed by the investigator, starts as soon as the subject is consented for the study. The safety surveillance and the safety reporting will continue until the last investigational visit has been performed, the subject/investigator concludes his participation into the study or the subject/investigator withdraws the subject from the study, except as otherwise specified in the CIP.

Records related to the subject's subsequent medical course must be maintained and submitted (as applicable) to the Sponsor until the event has subsided or, in case of permanent impairment, until the event stabilizes and the overall clinical outcome has been ascertained. All AEs will be monitored until they are adequately resolved. The status of the subject's condition should be documented at each visit.

AE data will be collected throughout the clinical study and will be reported to the Sponsor on a dedicated case report form through the EDC system. Reportable events to sponsor are considered:

1. ***All SAEs (whether or not the event is device and/or procedure related)***
2. ***All procedure, device and/or stimulation-related AEs (whether or not the event is considered serious)***

Device, procedure, and stimulation-related AEs are defined as follows:

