3.2 Adverse Events

All the adverse device effects, serious adverse device effects, UADEs, USADEs will be summarized for all subjects who enrolled in this trial in terms the number of events, the percentage of subjects with events and event rate as # event/patient-month per CEC adjudication.

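### The SAP's enrolment rule leaves abandoned trial implants out of the SAP 3.2 adverse-event table and makes the status of completed trial failures (up to 107 of 426 planned subjects) contradictory

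*SAP*

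**What the plan says.** **Enrolment.** SAP 1.3 states, for accounting, that "subjects are considered enrolled in the study only after they receive the trial system implant". Its next sentence reads "Subjects who fail the trial procedure are considered as screen failures".

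**Safety table.** SAP 3.2 covers ADEs, SADEs, UADEs and USADEs, as adjudicated by the CEC, and these "will be summarized for all subjects who enrolled in this trial". The abbreviation list in SAP 5.0 defines ADE and SADE so that procedure-related events are included. A complication of trial lead placement is therefore the kind of event this table should show.

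**Protocol.** Section 5.0 says "A maximum of 426 subjects will be enrolled to achieve 319 subjects with a permanently implanted system", and the synopsis says that these 426 "will undergo a trial of the neurostimulator system at up to 45 study sites". Section 7.0 describes the subjects in the study as "including system trial failures, those withdrawn from the clinical study and those lost to follow-up". Section 9.2 says that safety surveillance "starts as soon as the subject is consented for the study".

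**Trial-failure endpoint.** Both documents list a descriptive safety endpoint for adverse events of the trial implant procedure among subjects who fail the trial phase (Protocol 4.5 and 10.3; SAP 1.4.3 and 3.5.1). Protocol 10.3 analyses it in whoever has data. The closing sentence of SAP 3.5.1 limits it to the primary analysis population, which SAP 2.3.1 identifies as recipients of the permanent IPG.

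**The concern.** Under SAP 1.3, entry to the SAP 3.2 denominator depends on the exposure having succeeded. A subject taken to the procedure room, in whom lead placement is stopped by a complication, has had the invasive exposure but has not received a trial system. The complications most likely to end a procedure are then the ones most likely to be missing from the main device-effect table of a post-approval safety study.

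The second difficulty is the screen-failure label. In ordinary usage a screen failure is not an enrolled subject. Here the label is applied to people who may have had leads placed and used the trial stimulator. Whether they appear in SAP 3.2 would be settled by whoever programs the table, possibly after the data have been seen.

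**Working it through.** **1. Reproduce the planned flow.** Protocol 5.0 gives 426 enrolled, 319 permanently implanted, and attrition "to yield 287 subjects for the primary analysis at 12 months post-implant". The attrition rates are not visible, so they are inferred here, using N / (1 - d) rounded up:

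- 287 / (1 - 0.10) = 318.9, giving 319
- 319 / (1 - 0.25) = 425.3, giving 426

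Both stated figures are reproduced. The protocol's 426 therefore includes those who do not go on to permanent implant.

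**2. Apply the SAP wording to each type of subject.**

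| Subject | SAP 1.3, enrolment sentence | SAP 1.3, screen-failure sentence | In SAP 3.2? | In trial-failure endpoint under SAP 3.5.1? |
|---|---|---|---|---|
| Trial implant started, abandoned | Not enrolled | Screen failure, if counted as failing | No | No |
| Trial completed, failed | Enrolled | Screen failure | Unclear | No |
| Permanent IPG received | Enrolled | Does not apply | Yes | Does not apply |

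The first row does not depend on how the screen-failure sentence is read. The second row does.

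**3. Size of the second row.** 426 - 319 = 107, and 107 / 426 = 25.1%. This is an upper figure: it comes from a maximum enrolment, and it may include subjects who passed the trial but were not implanted. If the enrolment sentence governs, none of the 107 is lost.

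**4. Size of the first row.** The documents give no abandonment rate. As an assumption only, suppose 426 subjects receive the trial system and a share *a* of attempts is abandoned. The abandoned number is then 426 × a / (1 - a):

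- a = 0.5%: 426 × 0.005 / 0.995 = 2.1
- a = 5%: 426 × 0.05 / 0.95 = 22.4

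These subjects would be additional to the 426. The range says nothing about how many of them had an event.

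**5. Direction of effect for completed trial failures.** The percentage of subjects with an event across all 426 is a weighted average of the rates in the 319 and the 107. Leaving out the 107 lowers the reported percentage only if their rate is the higher of the two. As an illustration, take the ACCURATE Axium-arm SAE rates in Protocol 2.0: 10.5% overall for the implanted and 1.3% (system-trial phase) for trial failures.

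(0.105 × 319 + 0.013 × 107) / 426 = (33.50 + 1.39) / 426 = 8.2%

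Without the 107 the figure is 10.5%. On these inputs, omission raises the percentage. Events per patient-month could move either way, because trial failures contribute little follow-up. The inputs are all-cause SAEs, not device effects, so they serve only to show that the direction is not fixed.

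**The case against.** The strongest reply is that a subject who completes and fails the trial has received the trial system, and so is enrolled on the plain sense of the SAP's own sentence. Protocol 5.0 and 7.0 agree, and nothing visible says that a screen failure is removed from SAP 3.2. The phrase about failing the trial procedure might even mean a technical failure of placement. This stands. A reader might infer that a quarter of exposed subjects will certainly be lost; the documents support only that they could be. On the technical-failure reading, however, abandoned procedures are put outside enrolment all the more explicitly.

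Second, both documents have a dedicated endpoint for trial failures, and Protocol 10.7 has it summarised annually. That would be a real safeguard if its population fitted. As written in SAP 3.5.1, the population contains no trial failures. The endpoint also covers only trial-procedure events, not device or stimulation events during a failed trial.

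Third, part of the relevant text cannot be seen: Protocol 8.4, on the point of enrolment, ends in a redaction; SAP 2.1.1 is redacted; and SAP 1.3 has redacted blocks before the quoted sentences. These may bear on the matter, and no fault is inferred from them. The visible sentences still need to be aligned.

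Fourth, data collection is not at issue. Events are recorded from consent, and the CEC adjudicates them. This stands: the loss would be from the analysis table only.

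**Conclusion.** The point holds, with limits. For abandoned trial implants the gap follows directly from SAP 1.3 and 3.2. It is selective, and its size is unknown. For completed trial failures it is an unresolved contradiction affecting between 0 and 107 of 426 planned subjects (up to 25%), depending on whether a screen failure counts as enrolled.

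Three stronger readings are not supported:

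- **That the reported rates would be biased downward overall.** This is plausible for abandoned procedures. For completed trial failures the direction is uncertain, as the calculation shows.
- **That about one in eight subjects with an SAE would be lost**, from 1/76 in the trial phase against 8/76 overall in ACCURATE. Those are all-cause SAEs, whereas SAP 3.2 tabulates device effects. The trial-phase figure covers the whole arm, including subjects who went on to implant and would stay in the table. Protocol 2.0 reports only one related SADE in the Axium arm, and that was after implant.
- **That the primary endpoint is compromised.** It concerns permanent-implant recipients only and is not affected.

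**What to change.** Three wording changes in the SAP:

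- **SAP 3.2:** define the population as all subjects in whom a trial implant procedure was started, whether or not the system was placed or the trial succeeded.
- **SAP 1.3:** replace the screen-failure label with system trial failures, who remain enrolled.
- **SAP 3.5.1:** exempt the trial-failure adverse-event endpoint from the closing population sentence and give it its own population of trial failures, including abandoned procedures.

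The basis of the 426 cap need not change. The new wording should be checked against the unredacted Protocol 8.4 and SAP 2.1.1.

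No new data are required, since adverse events are already collected from consent. The cost is small: SAP 3.2 gains some subjects with short follow-up, and the reported procedure-related events may rise slightly.
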